### 1.3 Clinical Data to Date

Acetazolamide has previously been demonstrated to be efficacious in the treatment of ataxia symptoms in other genetic channelopathies including CACNA1A related disorder (Izquierdo-Serra et al. 2018). Acetazolamide has also been demonstrated to improve the cerebellar symptoms of PMM2-CDG over a six-month pilot study. This initial clinical trial in 24 patients ages 5 to 20 years (mean age  $12.3 \pm 4.5$  years, 9 females, 15 males) demonstrated that acetazolamide is well-tolerated and effective for motor cerebellar syndrome over six months in patients with PMM2-CDG (EudraCT 2017-000810-44). Subjects had statistically significant improvements in ICARS and Nijmegen Pediatric CDG Rating Scale (NPCRS) scores, and lower PATA rates. The PATA rate is the number of “pa – tas” an individual is able to speak in ten seconds. In this study, treatment with acetazolamide coincided with the gain of ability for some patients to sit and stand independently for a longer period of time, which caretakers rated to be an important clinical gain that significantly improved their quality of life and autonomy. Even patients with severe cerebellar atrophy (i.e., low MVRD) showed significant improvement in ICARS, demonstrating a potential therapeutic effect independent of structural cerebellar anomalies and atrophy. In fact, larger gains were observed in individuals with more severe ataxia demonstrated by higher baseline ICARS scores. There were no serious AEs related to the drug during the treatment. There was also no control group comparison, long term follow-up, nor ability to accurately titrate dose by mg/kg. An efficacious dosage of 22 mg/kg/day was established for optimal treatment response, although not all subjects were able to tolerate this dosage, leading to subject drop-out (Martinez-Monseny et al. 2019).

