### **Objective 3 (Secondary):**

**To examine the effect of acetazolamide on PMM2 biomarkers including carbohydrate deficient transferrin, electrolytes (Na, K, Cl, CO2), VBG (pH, pCO2, PO2, CO2, Base excess) or bicarbonate/CO2, liver function tests (AST, ALT, GGT, indirect and direct bilirubin, total protein, albumin, alkaline phosphatase), kidney function tests (BUN, Creatinine, Urinalysis, urine calcium/creatinine ratio, urine protein/creatinine ratio), growth (height, weight, head circumference), vital signs (blood pressure, respiratory rate, heart rate), PROMIS scores, dysarthria using the PATA score, and NPCRS score.**

We will collect these data at baseline and after 6 months of placebo or treatment and identify changes from baseline. We will analyze if there is a difference of changes between the treatment and placebo group. We will also compare baseline measurements to the last measurement obtained as part of the open label extension and determine if there are changes to these measurements.

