- If the investigator becomes aware of a likely related or related SAE, based on clinical judgement, the subject may be discontinued from placebo or drug. If an SAE occurs, the investigator will report the SAE to the DSMB. The DSMB will decide whether unblinding is necessary and convey their decision to the local study team, who will then implement the decision.

At Visit 5 (26 weeks) a discussion with the subject regarding whether they would like to proceed into the open label extension with acetazolamide will occur. If continuation is preferred, they will be restarted on dose 1 since we are not certain if they were on treatment or placebo. At subsequent visits after visit 5, acetazolamide will be modified in the same manner as above. If not, then neither drug nor placebo will be given to the patient. As this is an open label continuation, acetazolamide will be dispensed by a clinical pharmacy.

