### 7.2 Statistical Methods

#### Descriptive Statistics

Univariate descriptive statistics and frequency distributions will be calculated, as appropriate for all variables. Baseline values for demographic, clinical, and outcome variables (primary and secondary) will be tabulated for the treatment groups. These analyses will help identify potential confounding variables to be used as covariates in sensitivity analyses. Distributions across subgroups used in randomization will be qualitatively compared to assess whether the randomization was successful in equalizing distributions of these prognostic variables across treatment groups. Putative prognostic variables that will be investigated through these descriptive analyses include variables such as sex, baseline Mini-ICARS score, age, and baseline NPCRS score.

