### **Secondary Endpoint Analysis Approach:**

**Secondary Endpoint 1:** Incidence of (a) drug related adverse event(s) and (b) drug related serious adverse event(s) while they are on blinded therapy. The maximum grade for each type of adverse event will be summarized using the CTCAE v5.0. Using the safety set (see Section 7.3), the frequency and percentage of patients with a grade 1+ adverse event or serious adverse event classified as possibly, probably, or definitely related to the study treatment will be summarized by treatment arm. The frequency and percentage of patients who discontinue study treatment due to adverse events will also be reported by treatment arm. This analysis will be repeated to evaluate incidence of (a) drug related adverse event(s) and (b) drug related serious adverse event(s) for the duration that patients remain in the open label extension.

**Secondary Endpoint 2:** PMM2-Biomarker and other scores including:

- carbohydrate deficient transferrin results (Mono/Di, A/Di, Apo CIII1/Apo C III2, Apo CIII0/Apo CIII2),
- electrolytes (Na, K, Cl, CO2),
- VBG (pH, pCO2, PO2, CO2, Base excess) or bicarbonate/CO2,
- liver function tests (AST, ALT, GGT, indirect and direct bilirubin, total protein, albumin, alkaline phosphatase),
- kidney function tests (BUN, Creatinine, Urinalysis, urine calcium/creatinine ratio, urine protein/creatinine ratio),
- growth (height, weight, head circumference),
- vital signs (blood pressure, respiratory rate, heart rate),
- PROMIS scores,
- the PATA score,
- and NPCRS score.

As these endpoints are all numeric, and to identify if the post blinded therapy or final measurement of the open label extension is different from the baseline value, we will use a linear regression model to test if there is a change from baseline. Using the full analysis set (see Section 7.3), the between-arm mean difference in 6-month scores will be evaluated via a linear regression model predicting 6-month scores from baseline scores and treatment arm. This analysis will be repeated based on the final measurement of the open label extension. A nominal significance level of  $\alpha=0.05$  will be used for all analyses.

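### Open-label part of objective 3: the only contrast named is the arm difference, which cannot show a change shared by both arms. Objective 4: the non-responder rule gives no sign for the score difference, and its two conditions conflict or overlap at the planned means.

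*Combined protocol and SAP*

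**What the plan says.** **Objective 3, open label.** Section 2 undertakes to "compare baseline measurements to the last measurement obtained as part of the open label extension". Section 7.2, Secondary Endpoint 2, gives the purpose as "to identify if the post blinded therapy or final measurement of the open label extension is different from the baseline value" and continues "we will use a linear regression model to test if there is a change from baseline". It names no term, contrast or population for that test. The next sentence takes the full analysis set and specifies "a linear regression model predicting 6-month scores from baseline scores and treatment arm", with the between-arm mean difference as the quantity of interest. It then adds "This analysis will be repeated based on the final measurement of the open label extension". Under Section 5.2, patients who continue after Visit 5 all receive acetazolamide, and "they will be restarted on dose 1 since we are not certain if they were on treatment or placebo".

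**Objective 4.** The Exploratory Analysis paragraph of Section 7.2 defines non-responders among patients with at least 6 months of acetazolamide, taken in either the blinded or the open-label period. They must show no improvement in ataxia. They must also have a Mini-ICARS difference no greater than the placebo arm's average change. The paragraph does not say whether the difference is follow-up minus baseline or points of improvement. Correlations with baseline characteristics are then planned on the change from baseline to 6 months, without saying who enters.

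**The concern.** The extension supplies the long-term data that the pilot lacked. Of the pilot, Section 1.3 says "There was also no control group comparison, long term follow-up, nor ability to accurately titrate dose by mg/kg". The table of earlier studies records low bicarbonate in 9 of its 24 patients, and Section 1.5 names growth suppression as a concern. Bicarbonate and growth both belong to Secondary Endpoint 2. If either shifts in all continuing patients, the arm coefficient at the final visit stays near zero, and a null result could be read as no long-term change.

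For objective 4, the group meant to describe patients who do not respond could come out empty, could ignore its placebo benchmark, or could hold most of the treated patients, depending on a sign that is not written down. The correlations have a related problem. For a placebo-arm patient who first takes the drug in the extension, the change from baseline to 6 months is the placebo course, not a response to acetazolamide.

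**Working it through.** **Inputs.** Section 7.1 gives mean decreases of 6 points (acetazolamide) and 1.68 (placebo), an SD of change of 4 and 13 patients per arm. A higher score means worse ataxia (Section 1.3). Section 5.2 has treatment starting by week 1.5, and Section 6.5 places Visit 5 at weeks 21 to 34.

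**The plan's own figures.** 5.6 × 6/20 = 1.68 and 6 − 1.68 = 4.32. The two-sample t-test (noncentral t) has power 0.752 at 13 per arm and 0.715 at 12, so the 26 patients for 75% power are reproduced.

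**Open label.** Write the final score as a + b × baseline + c × arm + error. Adding a constant to every final score changes a and leaves c as it was.
- Simulation with 13 per arm (assumed baseline mean 25 and SD 8, residual SD 4): the arm test rejected in 4.65% of trials both with no change and with a shared 6-point fall. The arm coefficients were identical apart from rounding error.
- With change as the outcome and the same regressors centred, the intercept test rejected in about 100% of trials under the shared fall and 5.3% under no change. The model can therefore show a shared change, provided that contrast is declared.
- Power of a paired t-test for an assumed shared shift of 0.5 or 0.8 SD of change: 69% and 97% with 26 continuing, 56% and 92% with 20. The arm test stays at about 5%.

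**Non-responder rule.** Let C = follow-up − baseline, with C ~ N(−6, SD 4) on drug.
- *Signed change, both conditions.* C ≥ 0 and C ≤ −1.68 cannot both hold. With the placebo mean estimated from 13 patients, the group is empty in 99.0% of simulated trials with 13 treated patients and about 98% with 26.
- *Improvement-positive, both conditions.* Improvement ≤ 0 already implies improvement ≤ 1.68. Both together flag Φ(−6/4) = 6.7%, the same as the first alone. With the placebo mean estimated, the benchmark alters the group in 1.0% (13 treated) or 1.8% (26) of trials.
- *Second condition taken as the definition of the first.* Improvement-positive: Φ((1.68 − 6)/4) = Φ(−1.08) = 14.0%. Signed change: 1 − 0.140 = 86.0%.
- *Where this changes.* The conflict and the redundancy need the observed placebo mean to be an improvement. The chance that it is not is Φ(−1.68/(4/√13)) = 6.5%.
- *Single improvement-positive criterion, allowing for sampling of the placebo mean.* Φ(−4.32/√(16 + 16/13)) = 14.9%, or 1.9 of 13 and 3.9 of 26 patients. The second count assumes that delayed starters also improve by 6 points on average.

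**Correlation.** Suppose 13 placebo-arm patients enter with their placebo course alongside 13 treated. The pooled SD of change is √(16 + 4.32²/4) = 4.55. An assumed on-drug correlation of 0.60 becomes 0.60 × 0.5 × 4/4.55 = 0.26 if the characteristic is unrelated to placebo change, or 0.60 × 4/4.55 = 0.53 if it is equally related.

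**Exposure.** The shortest time on drug at Visit 5 for a patient who starts by the stated limit is 21 − 1.5 = 19.5 weeks, against the rule's 6 months.

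**The case against.** Section 7.2 does state a test of change from baseline that covers the final open-label measurement, and the between-arm sentence can be read as a second analysis. A reader might infer from the heading that the regression cannot detect a shared change at all. That is too strong, because the fitted mean at the average baseline, minus that average, comes from the same model. What stands is that this contrast is not declared, nor is its population: the full analysis set is defined by the 6-month visit, not by entry to the extension. The promise that "Univariate descriptive statistics and frequency distributions will be calculated, as appropriate for all variables" does not fill the gap.

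A shared shift would also not go unseen in individual patients. Acid-base results drive dose adjustment, growth is measured at least every 12 weeks, related adverse events are tabulated for the extension, and the DSMB reviews safety yearly. These reduce the risk but do not give a group estimate.

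A pooled change in cm and kg would mostly show normal growth in children. That objection is right, and the fix must use standardised scores.

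On objective 4, the empty group needs the less natural sign. Section 7.1 speaks of points of improvement, and on that scoring the rule is coherent with a harmless, redundant benchmark. A reader might infer that the rule will flag nobody; the text supports that only under signed change with both conditions required. Likewise, the text does not say that placebo-course data will enter the correlations. It leaves this open.

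**Conclusion.** The point holds as a gap in specification with a better analysis readily available. For a stated secondary objective, the one contrast named at the final open-label visit is blind to a change common to both arms, and the contrast that would show it is not declared. For an exploratory objective, the missing sign and the two joined conditions produce results from an almost always empty group to 86% of treated patients. The most natural reading flags 6.7% and makes no use of the placebo benchmark.

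The rule figures rest on the planned means and SD, normality and, in nearly all cases, an observed placebo mean that is an improvement. The paired-test powers and the correlation figures are illustrations that rest on assumed shifts, correlations and numbers continuing. A reader might infer that the trial's main result is at risk. It is not: the primary analysis, the sample size of 26 and the blinded 6-month regression are unaffected. The change should be made before unblinding.

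**What to change.** In Section 7.2, Secondary Endpoint 2:
- In patients who enter the extension, estimate within-patient change from baseline to the final open-label measurement with a 95% CI, pooled and by original arm.
- For height, weight and head circumference in children, use age- and sex-standardised z-scores.
- Report the result as uncontrolled, label any arm contrast as early versus delayed start, and keep the blinded 6-month regression.

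In the Exploratory Analysis:
- Define improvement as the last score before acetazolamide minus the on-drug score: Visit 1 minus Visit 5 for the active arm, and Visit 5 minus Visit 9 for placebo-arm patients who start in the extension.
- Use one criterion: improvement at or below the placebo arm's mean improvement in the blinded phase.
- Apply one exposure definition to both original arms, reconcile it with the Visit 5 window, and report weeks on drug.
- Run the correlations on the on-drug change and state who enters.
- With only about 2 to 4 patients likely to be flagged, describe the group and rely on the continuous change.

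The cost is a few sentences, with no new visits or data. Three limits remain and should be stated: the open-label change has no control, time on drug varies, and open-label scores are set against a blinded benchmark.

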## Handling of Intercurrent Events

Per the E9(R1) guidance (*Statistical Principles for Clinical Trials; Addendum: Estimands and Sensitivity Analysis in Clinical Trials*), a treatment policy strategy will be used to address intercurrent events. That is, for the primary analysis, each patient's change in Mini-ICARS score from baseline to 6 months will be used regardless of whether an intercurrent event occurs.

## Handling of Missing Data

Attempts to minimize missing data will be made through site training and data monitoring (e.g., form delinquency notifications, data queries). Patients who prematurely discontinue study treatment will be encouraged to remain in the study for their scheduled efficacy and safety assessments. The primary analysis evaluating the between-arm mean difference in the change in Mini-ICARS score from baseline to 6 months will include all patients with a baseline and 6-month Mini-ICARS score. For patients with a missing Mini-ICARS score at 6 months, imputation will be used as part of a sensitivity analysis. Specifically, all patients with a missing Mini-ICARS score at 6 months will be assumed to have no change in Mini-ICARS score from baseline to 6 months (i.e., 0 imputed for all missing change scores).

## Multiplicity

No adjustment for multiplicity will be made, though interpretation will take into consideration that the type I error is strictly controlled for the primary endpoint only. Overall interpretation will also take into consideration consistency of results across analyses.

## Interim Analysis

No interim analysis will be conducted.

## 7.3 Subject Populations for Analysis

- *Intent-to-treat set*: All randomized patients, regardless of whether they received their assigned study treatment.
- *Full analysis set*: All randomized patients who complete the baseline and 6-month visits.
- *Safety set*: All randomized patients who receive at least one dose of acetazolamide or placebo.
- *Per-protocol set*: All randomized patients who report taking at least 4 weeks of their assigned study treatment and complete the baseline and 6-month visits.

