#### 4.4 Subject Withdrawal Criteria

- Failure of subject to adhere to protocol requirements
  - If a patient is unable to adhere to study procedures, they may be withdrawn from the study by the investigator per investigator discretion.
- Subject decision to withdraw from the study (withdrawal of consent)
  - A patient or patient's family/guardian may withdraw consent at any time and cease administration of study drug or placebo. They may be asked to return for follow up testing to ensure that laboratory values are satisfactory (see schedule of events table (SOE)) and please refer to section 6.10.

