## 5.6 Prior and Concomitant Therapy

- All concomitant medication and concurrent therapies (physical therapy (PT)/occupational therapy (OT)/speech therapy (ST)/feeding therapy (FT)) will be documented at baseline and at each visit (from 30 days prior to the first dose).
  - Medication trade name;
  - Indication for which the medication was given;
  - Dose/strength, route, and frequency of administration;
  - Date started and date stopped (or continuation at study exit).
- All medications that do not have a high risk of serious reactions will be permitted while on the study. Any medication listed as an exclusion criterion is not permitted while on the study (i.e., Mecamylamine, Sodium Phosphates, Salicylates, Mefloquine, Methenamine and other Carbonic Anhydrase Inhibitors).
- If a subject has started taking a prohibited medication on the exclusion criteria, they will be discontinued from the study. If a subject is started on a medication that has a high risk of serious reaction, continued participation in the study will be decided on a case-by-case-basis.

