### 5.7.1 Blinding of Study

- Investigators, study staff in contact with patients, and subjects will be blinded. The research pharmacy will then dispense acetazolamide or placebo to the patient or study staff. Access to the randomization code will be strictly controlled by the research pharmacy and DMCC. Packaging, labeling, and appearance of the test and control treatments will be similar to maintain the blinding. Active drug concentrations will be prepared by the pharmacy prior to handoff to clinicians or patients/caretakers for administration. The study will proceed to open label continuation at Visit 5 (Week 40-56). During the study, the blind may be broken only in emergencies when knowledge of the patient's treatment group is necessary for further patient management. If the blind is broken for a subject, that individual will be removed from the blinded portion of the study. If a subject experiences an adverse event warranting unblinding procedures, the pharmacy will inform the physician of the prescribed treatment.

After all data are collected for the blinded portion of the study and all data cleaning is completed for these data, the data base for the blinded portion of the study will be locked and the study will be unblinded for analysis.

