#### Primary Endpoint Analysis Approach:

**Primary Hypothesis:** The administration of acetazolamide will improve the ataxia symptoms in patients with PMM2-CDG. **Primary Endpoint:** Change in Mini-ICARS score from baseline to 6 months.

The primary analysis will be conducted using the full analysis set (see Section 7.3). The between-arm mean difference in the change in Mini-ICARS score from baseline to 6 months will be evaluated via a two-sample t-test. The primary analysis will include all patients with a baseline and 6-month Mini-ICARS score. As a sensitivity analysis, all patients with a missing Mini-ICARS score at 6 months will be assumed to have no change in Mini-ICARS score between baseline and 6 months. A per-protocol analysis will also be conducted using the per-protocol set (see Section 7.3). A nominal significance level of  $\alpha=0.05$  will be used for all analyses.

**Exploratory Analysis:** To explore characteristics of individuals with PMM2-CDG who do not respond to acetazolamide (objective 4), we will define the subgroup of individuals who received at least 6 months of acetazolamide and did not have an improvement in ataxia. These individuals could have received acetazolamide during either the blinded period or open label extension period for at least 6 months. In addition, their Mini-ICARS score difference after being on acetazolamide for at least six months was at or less than the mean Mini-ICARS score change for the placebo group. A correlation analysis for change in Mini-ICARS from baseline to 6 months will be performed with each of the baseline characteristics. These baseline characteristics include age, sex, weight, height, head circumference, NPCRS score, Mini-ICARS score, PATA score, concomitant medication list, allergies, current ability with activities of daily living, laboratory

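### Subjects taken off the study may have no 6-month Mini-ICARS, so the treatment-policy strategy is not assured for them, and one zero-change imputation does not show how much the result depends on them

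*Combined protocol and SAP*

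**What the plan says.** **Strategy.** Section 7.2 (Handling of Intercurrent Events) adopts a treatment-policy strategy: each patient's 6-month change in Mini-ICARS "will be used regardless of whether an intercurrent event occurs".

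**Who is analysed.** The full analysis set in section 7.3 is "All randomized patients who complete the baseline and 6-month visits", and section 7.2 adds: "The primary analysis will include all patients with a baseline and 6-month Mini-ICARS score". An intent-to-treat set is defined, but no analysis in section 7.2 names it. The per-protocol set also requires the 6-month visit.

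**Keeping patients in.** Section 7.2 (Handling of Missing Data): "Patients who prematurely discontinue study treatment will be encouraged to remain in the study for their scheduled efficacy and safety assessments".

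**Ways off the study.**
- Section 5.6: "If a subject has started taking a prohibited medication on the exclusion criteria, they will be discontinued from the study".
- Section 5.7.1: "If the blind is broken for a subject, that individual will be removed from the blinded portion of the study".
- Section 4.4, on a patient who cannot keep to study procedures: "they may be withdrawn from the study by the investigator per investigator discretion".

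**After leaving.** The early termination visit (section 6.10 and the last column of Table 3) has blood tests and interview items but no Mini-ICARS. ICARS scores are sought only from clinical records, where these exist.

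**Missing scores.** The one sensitivity analysis for missing scores has "0 imputed for all missing change scores", in both arms.

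**The concern.** A treatment-policy analysis needs the outcome after the intercurrent event. The plan protects that outcome for patients who stop study drug and stay in the study. It has no matching rule for those who leave the study because of a prohibited medication, a broken blind or non-adherence. If Visit 5 is not done for them, they fall out of the primary analysis, and the comparison becomes one of completers.

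The loss cannot be repaired later. A clinical ICARS recorded item by item would contain the nine Mini-ICARS items (section 1.3), but nothing ensures that one exists near month 6. Enrolling replacements under section 3.2 restores the number of completers, not the missing outcomes.

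The zero-change check is then the only view of what the missing patients might do to the result. Section 7.1 expects improvement in both arms, so zero is a particular assumption in each arm. It can err in either direction.

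**Working it through.** **Inputs.** Section 7.1: expected improvement 6 points on drug and 5.6 × 6/20 = 1.68 on placebo, difference 4.32; SD of change 4; two-sided alpha 0.05; power 75%; 13 per arm. Section 3.2: 26 evaluable patients, 20% loss, maximum 33. Improvement is counted as positive below. The numbers missing and the outcomes of leavers are assumptions, because the documents give neither.

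**The plan's own figures.** The two-sample t-test has 71.5% power at 12 per arm and 75.2% at 13, so 26 in total reproduces. 26/0.80 = 32.5, which rounds up to 33. No stated figure is wrong.

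**Step 1: does each route end in a missing score?**

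| Route | What the text settles | Reading |
|---|---|---|
| Prohibited medication (5.6) | Participation ends, without discretion | Clear conflict with section 7.2 |
| Broken blind (5.7.1) | Subject leaves the blinded portion; silent on whether Visit 5 is scored and used | Ambiguity |
| Non-adherence to procedures (4.4) | Withdrawal possible, at discretion; for poor drug compliance, 5.5 only encourages adherence | Weaker route |

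**Step 2: direction of the zero-change error.** Let p_a and p_p be the shares lost on drug and placebo, and La and Lp the true mean improvements of those lost.

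- Treatment-policy difference = 6(1−p_a) + p_a·La − [1.68(1−p_p) + p_p·Lp]
- Zero-change difference = 6(1−p_a) − 1.68(1−p_p)
- Zero-change minus treatment-policy = p_p·Lp − p_a·La

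| Assumed loss | La | Lp | Treatment-policy | Zero-change | Error |
|---|---|---|---|---|---|
| 10% drug only | 1.68 | – | 3.89 | 3.72 | −0.17 |
| 20% drug only | 1.68 | – | 3.46 | 3.12 | −0.34 |
| 20% per arm | 6 | 1.68 | 4.32 | 3.46 | −0.86 |
| 20% per arm | 0 | 1.68 | 3.12 | 3.46 | +0.34 |
| 20% drug only | −3 | – | 2.52 | 3.12 | +0.60 |

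The completer difference is 4.32 in every row. Zero change can be too low or too high for the drug. For scale, the standard error at 13 per arm is 4·√(2/13) = 1.57.

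**Step 3: tipping points.** Take 13 completers per arm at the planned means with SD 4: t = 4.32/1.569 = 2.75 on 24 df, p=0.011. Add k missing patients to an arm with completer mean m, all set to a constant v:

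- arm mean = (13m + kv)/(13 + k)
- arm sum of squares = 12·4² + [13k/(13 + k)]·(m − v)²
- pooled SD = √(sum of both arms' sums of squares / total df), then the ordinary t-test.

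Four missing on drug, three on placebo, all at zero:
- means: 78/17 = 4.588 and 21.84/16 = 1.365; difference 3.22
- sums of squares: 192 + (52/17)·36 = 302.1 and 192 + (39/16)·1.68² = 198.9
- pooled SD √(501.0/31) = 4.02; SE 4.02·√(1/17 + 1/16) = 1.40; t = 2.30, p=0.028.

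Now set placebo leavers to 1.68 and lower the drug leavers until p reaches 0.05. At v = −0.21 the difference is (78 − 0.84)/17 − 1.68 = 2.86 with SE 1.40, so t = 2.04, the critical value on 31 df.

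| Missing, drug/placebo | Zero-change p | Drug leavers' mean at which p = 0.05 (placebo leavers 1.68) |
|---|---|---|
| 1/1 | 0.014 | about 6.0 points worse than baseline |
| 2/2 | 0.016 | about 2.5 worse |
| 4/3 | 0.028 | about 0.2 worse |
| 5/2 | 0.053 | already above 0.05 at zero change |
| 6/1 | 0.092 | already above |
| 7/0 | 0.148 | already above |

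A constant imputation understates variability. Giving the imputed values an SD of 4 moves the 4/3 tipping value to about 0.7 points of improvement.

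**The case against.** The other side has a good case on several points.

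- **Most intolerance is covered.** A reader might infer that treatment policy fails for anyone who stops the drug. It does not: section 7.2 asks those patients to stay for assessments. Section 1.3 reports drop-out from intolerance in the pilot study, but intolerance is none of the three routes, so that drop-out is not evidence of loss through them.
- **The routes differ in strength.** Nothing in section 5.7.1 cancels Visit 5, and a score that is taken would be used under section 7.2. Section 4.4 is discretionary, and a patient who cannot follow procedures may not manage Visit 5 anyway. Only section 5.6 clearly ends participation.
- **The plan claims no worst case.** A reader might take zero change to be offered as the most pessimistic assumption. The plan calls it a sensitivity analysis and nothing more. The gap is that it stands alone.
- **Zero change is not blind to fragility.** With 5/2, 6/1 or 7/0 missing it loses significance by itself. The claim that it never separates a fragile result from a robust one would be wrong.
- **Seven missing outcomes is an upper case.** The allowance in section 3.2 also covers ineligibility, cancellation and major treatment violation. A violator who attends Visit 5 stays in the full analysis set. The same caution applies to the 20% rows.
- **The errors are modest.** Those in Step 2 run from −0.86 to +0.60, at most about 0.55 of the standard error of 1.57.

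All of this limits the size of the point. It does not supply a Visit 5 score for a subject discontinued under section 5.6, and it does not show the reader how far a result under near-balanced loss depends on those who left.

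**Conclusion.** The concern holds as a minor one, in two parts.

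First, the treatment-policy strategy is not assured for subjects taken off the study. Section 5.6 conflicts with it, section 5.7.1 leaves it open, and section 4.4 permits a further loss. The early termination visit does not fill the gap.

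Second, zero change flags strongly uneven loss on the drug arm but does not show fragility when loss is near-balanced. It is significant with 1/1, 2/2 and 4/3 missing (p=0.014, 0.016 and 0.028), while the outcome that would overturn the result moves from about 6.0 to 2.5 to 0.2 points worse than baseline.

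These sizes rest on the planned means and SD, constant imputation, placebo leavers at 1.68 and assumed counts of missing patients. The documents give no loss rate by arm or by route. It would go beyond them to say that the primary result will be biased, or biased in favour of the drug.

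**What to change.** 1. **Reconcile sections 5.6, 5.7.1 and 4.4 with section 7.2.** State that a subject who starts a prohibited medication, is unblinded or is withdrawn for non-adherence still has the scheduled Visit 5 Mini-ICARS where consent allows, and is analysed in the randomised arm. This concerns follow-up only and takes no position on when study drug is stopped.
2. **Keep the zero-change analysis and add one tipping-point analysis.** Run it over all randomised patients, with separate shifts for the two arms and an imputation that carries variability. It also covers families who withdraw consent, whom the first change cannot reach.

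The cost is some protocol and SAP wording, a few more Visit 5 assessments of a kind already scheduled, and one extra sensitivity analysis. The estimated effect may be slightly smaller once these subjects are included.
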